Delayed Surveillance Colonoscopy following Piecemeal EMR – a Randomized Study

Study approval Number- RMB-0069-25

Document Date- 17/12/2025

Abstract

Background

Colorectal cancer (CRC) is a major cause of cancer-related morbidity and mortality. Piecemeal endoscopic mucosal resection (pEMR) is an effective treatment for large non-pedunculated colorectal polyps (LNPCPs), which are high-risk precursors of CRC. Previous data have shown that residual and recurrent adenoma (RRA) may occur in 15–30% of cases following pEMR. Accordingly, current guidelines recommend intensive follow-up, which can cause patient morbidity and lack of compliance and financial healthcare burdens. Recent advances in EMR techniques, particularly margin ablation, have significantly reduced RRA rates to approximately 5%. In a recent retrospective analysis, we found that delayed surveillance (12 months post-EMR) was not associated with higher recurrence rates compared to early surveillance (3–6 months). This prospective randomized trial aims to confirm and validate these findings.

Objectives and Hypotheses

To evaluate whether a relaxed surveillance strategy involving fewer colonoscopies (12 and 48 months) is non-inferior to the standard intensive strategy (6, 18, and 48 months) in management of residual or recurrent disease.

Hypothesis: A relaxed surveillance protocol does not increase the rate of residual or recurrent adenoma detected at long-term follow-up, in patients undergoing pEMR of LNPCPs with margin ablation.

Methods

This multicenter prospective randomized controlled trial will enroll approximately 760 patients undergoing pEMR for LNPCPs at Rambam Health Care Campus, Tel Aviv Sourasky Medical Center (Ichilov Hospital), Nazareth Holy Family Hospital and HaEmek Medical Center (Afula). Detailed clinical, endoscopic, and histologic data will be collected on lesion morphology, size, histopathology, and procedural techniques.

Patients will be randomized into two surveillance groups: **the Standard Surveillance Group**: Colonoscopies at 6, 18, and 48 months after the index procedure and **the Relaxed Surveillance Group**: Colonoscopies at 12 and 48 months after the index procedure (similar to surveillance protocols following en-bloc excision by ESD)

Significance and Relevance to Cancer Care

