Recent data suggests that RRA can be significantly reduced by systematically applying ablative measures to the post-EMR resection margin. Multiple studies show that in expert hands, the risk of RRA at SC1 can be reduced to 3-5% [6,7,8,12,13]. Currently, an intensive follow-up schedule is recommended following pEMR, with SC1 performed 3-6 months after the initial procedure and SC2 one year after SC1. However, this intensive follow-up places additional burdens on both patients and the healthcare system and may hinder patient compliance [9]. Given that with the advent of margin ablation, RRA rates at SC1 are extremely low, the impact of early surveillance on long-term recurrence rates may be minimal.

We recently completed a retrospective study to evaluate this hypothesis. The study showed no significant difference in recurrence rates between the standard group, which underwent surveillance after 3-6 months, and a group of patients who had delayed surveillance (mean follow-up of 11 months).

The aim of this study is to confirm and validate these findings, in a prospective randomized study. This will solidify the results we observed in our previous retrospective study and potentially lead to a less intensive surveillance strategy.

Methods

Study Design:

We will conduct a multicenter, prospective, non-inferiority randomized study in four academic centers in Israel: Rambam Health Care Campus, Tel Aviv Sourasky Medical Center (Ichilov Hospital), Nazareth Holy Family Hospital and HaEmek Medical Center. Following complete pEMR of a LNPCP, participants will be randomly assigned to either the standard surveillance protocol or the relaxed surveillance protocol. Patients will be consented prior to the EMR procedure.

Randomization – computer-generated dynamic block randomization with a 1:1 allocation ratio will be performed to achieve balance of multiple baseline covariates including: demographic data, procedural data, and lesion characteristics.

Patients:

We will include adult patients who undergo pEMR for LNPCPs (≥ 20 mm) and provide informed consent. Inclusion criteria include

- Adults aged 18 years and older.
- Undergoing pEMR of LNPCPs.
- Able to provide informed consent and comply with follow-up requirements.

Exclusion criteria include:

- Patients with invasive cancer identified during the index procedure.
- en bloc resection.
- Patients unable to attend follow-up colonoscopies due to comorbid conditions.

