- Patients who require additional surgery for polyp removal or other complications.

Informed Consent:

Before enrollment, each patient will receive a detailed explanation about the study. They will be given the opportunity to ask questions and discuss any concerns. Written informed consent will be obtained from all participants prior to any study-related procedures.

Procedures:

All pEMR procedures and surveillance colonoscopies will be performed by experienced endoscopists trained in pEMR techniques. Specifically, [name] was lead author on the randomized trial on margin ablation [13] and practiced this technique routinely since early 2016. Procedures will be conducted using high-definition endoscopes (Olympus 190 series Q190 PCF/CF or Fuji 760 series), following a standardized protocol:

1. Inspection and photo documentation of LNPCPs with high-definition white light (HDWL) and optical chromoendoscopy before resection to exclude features suggestive of deep submucosal invasion.
2. Standard pEMR technique with the objective of complete snare excision, using sub-mucosal injections of Succinylated Gelatine (Gelofusin) or Normal Saline and braided snares of various sizes.
3. Thermal ablation of the mucosal defect margin using snare soft tip coagulation (STSC) to create a 2- to 3-mm rim of ablated tissue.

Groups and Follow-Up:

- Standard Surveillance Group: Patients will undergo surveillance colonoscopy at 6 and 18 months after the index procedure. The standard surveillance group will have an additional colonoscopy at 48 months in order to converge the timeline with the delayed group.
- Relaxed Surveillance Group: Patients will undergo surveillance colonoscopy at 12 and 48 months after the index procedure.

Data Collection:

We will collect demographic data, lesion characteristics, procedural details, and surveillance outcomes. All recurrences will be identified using endoscopic evaluation. Routine biopsies will be taken only when recurrence is suspected endoscopically, based on a validated approach that has shown a negative predictive value (NPV) of 99% for identifying normal scars without recurrence [14].

Data Management, Storage and Security:

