All data will be collected on data collection forms. These will be stored in a locked cabinet at the Gastroenterology department. This data will be entered into electronic data sheets (Excel and Redcap). The electronic files will be password protected and stored on a password-protected computer in the Gastroenterology department. Access to the data will be given to the study investigators and the study research assistant.

Primary Endpoint

The primary endpoint is the rate of residual or recurrent adenoma at the second surveillance colonoscopy (SC2), comparing the relaxed and standard surveillance groups.

Secondary Endpoints

Secondary endpoints include: recurrence rates at SC1; risk factors associated with recurrence; subgroup analysis of high risk lesions (e.g., high-grade dysplasia, sessile serrated morphology); rates of new or missed polyps at SC2; adverse events related to EMR or surveillance procedures; and comparative cost effectiveness of both surveillance strategies.

Timetable

We anticipate 4-5 years are required to complete the study: 1-2 years for recruitment and an additional 36 months for follow-up to SC2.

Funding and Competing Interests

There are no disclosures. No commercial funding is sought. We will apply for research grants to help with study funding, specifically research assistant salary and management of the electronic database.

References:

1. Siegel, R. L. et al. Colorectal cancer statistics, 2020. *CA. Cancer J. Clin.* 70, 145–164 (2020).
2. Zauber, A. G. et al. Colonoscopic polypectomy and long-term prevention of colorectal-cancer deaths. *N. Engl. J. Med.* 366, 687–96 (2012).
3. Ferlitsch, M. et al. Colorectal polypectomy and endoscopic mucosal resection (EMR): European Society of Gastrointestinal Endoscopy (ESGE) Clinical Guideline. *Endoscopy* 49, 270–297 (2017).
4. Jayanna, M. et al. Cost Analysis of Endoscopic Mucosal Resection vs Surgery for Large Laterally Spreading Colorectal Lesions. *Clin. Gastroenterol. Hepatol.* 14, 271-8 (2016).
5. Bahin, F. F. et al. Wide-field endoscopic mucosal resection versus endoscopic submucosal dissection for laterally spreading colorectal lesions: a cost-effectiveness analysis. *Gut* 67, 1965–1973 (2018).

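### The secondary endpoint on new or missed polyps is read at month 18 in one arm and month 48 in the other, so the relaxed arm is expected to show an excess even if polyp incidence is the same

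*Protocol*

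**What the plan says.** The Protocol's Secondary Endpoints section lists "rates of new or missed polyps at SC2", with no calendar month and no allowance for the length of the interval.

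SC2 is introduced under Primary Endpoint as "the second surveillance colonoscopy (SC2), comparing the relaxed and standard surveillance groups". That is a position in a sequence, not a fixed time.

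Groups and Follow-Up sets the visits:

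- Standard arm: "Patients will undergo surveillance colonoscopy at 6 and 18 months after the index procedure".
- Relaxed arm: "Patients will undergo surveillance colonoscopy at 12 and 48 months after the index procedure".
- Standard arm again: "The standard surveillance group will have an additional colonoscopy at 48 months in order to converge the timeline with the delayed group".

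The Background uses the same labels when it describes current practice: "SC1 performed 3-6 months after the initial procedure and SC2 one year after SC1". The Timetable allows "an additional 36 months for follow-up to SC2".

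**The concern.** Counted in order, the standard arm's second surveillance examination is at month 18 and the relaxed arm's is at month 48. The standard arm's month-48 examination is its third, and no endpoint is tied to it.

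A polyp counted as new at SC2 has had the time since SC1 in which to appear. If that time differs between arms, so does the expected count, whatever the surveillance strategy does. The trial asks whether fewer colonoscopies are acceptable, and polyps away from the scar are a natural safety check on that question. As written, the endpoint would tend to count against the relaxed strategy even if it did no harm, and a real harm could not be separated from the longer interval.

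**Working it through.** **Inputs.** The visit months are from Groups and Follow-Up. The sample size is from the Abstract ("will enroll approximately 760 patients undergoing pEMR for LNPCPs"), and the 1:1 allocation from Study Design gives about 760 / 2 = 380 per arm. The Protocol states no polyp incidence, miss rate or expected result for this endpoint, so there is no planned figure to reproduce. The incidences below are assumptions.

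**Step 1: intervals, with no assumption needed.**

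- Standard arm, SC1 to SC2: 18 − 6 = 12 months.
- Relaxed arm, SC1 to SC2: 48 − 12 = 36 months.
- Ratio: 36 / 12 = 3.

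**Step 2: expected SC2 proportions when incidence is the same in both arms.** With a constant rate r per patient-year, and SC1 clearing what was present, the proportion with at least one new polyp after t years is 1 − exp(−r × t).

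| Assumed r | Standard, t = 1 | Relaxed, t = 3 | Excess in relaxed arm (points) |
|---|---|---|---|
| 0.05 | 4.9% | 13.9% | 9.0 |
| 0.10 | 9.5% | 25.9% | 16.4 |
| 0.20 | 18.1% | 45.1% | 27.0 |

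At a lower incidence the excess shrinks. If 2% of patients develop a polyp in 12 months, the 36-month figure is 1 − 0.98³ = 5.9%, an excess of 3.9 points.

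**Step 3: chance that the excess looks significant.** With 380 per arm and a two-sided 5% comparison of proportions, a 12-month rate of 2% gives a 79% chance of a nominally significant difference. A rate of 5% gives 99%, and 10% or more gives over 99%. These figures are for new polyps alone.

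**Step 4: adding missed polyps.** At SC2 both arms have had two earlier examinations (index and SC1), so take an equal share m with a missed polyp in each arm. The proportion becomes 1 − (1 − m)(1 − p), and the difference between arms is (1 − m)(p36 − p12). Missed polyps therefore scale the excess down and cannot create or reverse it. For a 12-month rate of 10% (p36 = 27.1%):

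- m = 5%: 14.5% against 30.7%, an excess of 16.2 points.
- m = 25%: 32.5% against 45.3%, an excess of 12.8 points.

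The chance of a significant result stays at 95% or above in that range. At a 12-month rate of 2% it falls to between 14% and 44%.

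**Step 5: the alternatives at a common horizon.**

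- Cumulative to month 48: with equal incidence and complete detection, both arms are expected to reach 1 − exp(−4r), which is 18.1%, 33.0% or 55.1% for the three rates. The expected difference is zero.
- At the month-48 examination only: the time since the last examination is 48 − 18 = 30 months (standard) and 48 − 12 = 36 months (relaxed). The proportions are 11.8% against 13.9%, 22.1% against 25.9%, and 39.3% against 45.1%, a difference of about 2 to 6 points.

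**The case against.** **Intent.** The strongest reply is that the sponsor means SC2 to be the month-48 visit. The added standard-arm colonoscopy is there to bring the two timelines together, and the Abstract's hypothesis concerns long-term follow-up. This makes an untied label more likely than a deliberate 12-against-36-month comparison. It does not redefine SC2. The added visit is third in order, and the Background places SC2 one year after SC1 under the standard schedule. The Timetable's 36 months matches neither month 18 nor month 48 from the index procedure.

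**Overlap with the primary endpoint.** The same label carries the same mismatch into the primary endpoint, where it matters more. Fixing SC2 at month 48 for both would remove the mismatch here too. That stands. The polyp endpoint still needs its own wording, because it concerns lesions that arise over time away from the scar.

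**What a reader might infer beyond this.** Three stronger readings are not supported.

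- That month 48 would not repair the endpoint, because 30 against 36 months remains. At month 48, time since the index procedure is equal, and the date of the last examination is part of the randomised strategy. The 2 to 6 points in Step 5 would be an effect of strategy at a common time, not an artefact.
- That missed polyps are themselves distorted because most would be found at SC1. The Protocol gives no miss rate and does not limit missed polyps to those overlooked at the index procedure.
- That a false excess is certain. Its size depends wholly on an unstated incidence. The endpoint sentence also names no test, although comparing the arms is its evident purpose in a two-arm trial.

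**Conclusion.** The concern holds. Read as written, the endpoint compares arms over SC1-to-SC2 intervals of 12 and 36 months, and for any positive incidence of new polyps the expected bias runs against the relaxed arm. The interval mismatch follows from the Protocol alone. The size does not: about 9 to 27 percentage points rests on a constant incidence of 0.05 to 0.20 per patient-year, equal in both arms, with SC1 clearing what was present. At lower incidence, or with a large share of missed polyps, the excess is smaller and may not reach significance. The Protocol itself fixes both the visit label and the schedule, so an analysis plan that followed them would inherit the problem.

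**What to change.** Do not compare the arms by visit number. Define the endpoint over a common horizon, in one of two ways:

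1. the cumulative proportion of patients with at least one new or missed polyp away from the EMR scar, across all examinations through month 48; or
2. the proportion with such a polyp at the 48-month colonoscopy, in both arms.

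The first counts everything found over the same 48 months. The second measures what each strategy leaves present at the same time point, including the effect of its last examination. Choose one before any outcome data are seen.

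Do not add a between-arm comparison of polyps first seen at SC1. SC1 is at month 6 in one arm and month 12 in the other, which repeats the fault: with the same assumed rates, 2.5% against 4.9%, 4.9% against 9.5%, and 9.5% against 18.1%.

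The cost is a reworded endpoint and one re-specified table. Neither version changes the visit schedule or adds a colonoscopy. The cumulative version has two downsides to state beside the result. The standard arm has three looks and the relaxed arm two, so incomplete detection can favour finding more in the standard arm. It also needs polyps away from the scar recorded at every examination. Data Collection mentions surveillance outcomes only in general terms, so the case forms should be checked for this.

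### The timetable allows 36 months of follow-up, but the visit schedule runs to month 48 in both arms, so the stated 4-5 years is 12 months too short

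*Protocol*

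**What the plan says.** The Timetable section gives a total and its two parts: "We anticipate 4-5 years are required to complete the study: 1-2 years for recruitment and an additional 36 months for follow-up to SC2".

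The visit schedule appears in the abstract and again under Groups and Follow-Up:

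- Relaxed arm, abstract: "Colonoscopies at 12 and 48 months after the index procedure". Groups and Follow-Up agrees: "Patients will undergo surveillance colonoscopy at 12 and 48 months after the index procedure".
- Standard arm, abstract: "Colonoscopies at 6, 18, and 48 months after the index procedure". Groups and Follow-Up gives the first two examinations as "Standard Surveillance Group: Patients will undergo surveillance colonoscopy at 6 and 18 months after the index procedure" and then adds a third: "The standard surveillance group will have an additional colonoscopy at 48 months in order to converge the timeline with the delayed group".

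The primary endpoint is assessed at the second surveillance colonoscopy (SC2). The Study Design section places randomisation after complete piecemeal resection, so a patient's entry to the trial and month 0 practically coincide.

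**The concern.** The timetable counts 36 months from the end of recruitment to SC2. Under the schedule no examination falls at month 36 in either arm, and the relaxed arm's second examination is at month 48. The 36 is not an isolated misprint, because it carries through to the 4-5 year total.

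Three things are at stake, in decreasing order of certainty:

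- **Study length.** The stated time to completion is shorter than the protocol's own schedule requires.
- **Funding.** The Funding and Competing Interests section says grants will be sought, "specifically research assistant salary and management of the electronic database". The protocol shows no budget. One built on this timetable would lack the year in which the last month-48 examinations fall due.
- **Endpoint data.** If the study did close 36 months after the last enrolment, the later-recruited patients would not yet be due for their month-48 examination, which in the relaxed arm is the primary-endpoint examination.

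**Working it through.** **Inputs**

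- Recruitment period A: 12 to 24 months (Timetable).
- Follow-up allowed after recruitment: 36 months (Timetable).
- Last scheduled examination: month 48 in both arms (abstract; Groups and Follow-Up).
- Relaxed arm: examinations at months 12 and 48. Standard arm: months 6, 18 and 48.
- Sample size about 760 (abstract), allocated 1:1 (Randomization), so about 760 / 2 = 380 per arm.

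**Step 1: reproduce the stated total.** Total = A + 36. This gives 12 + 36 = 48 months and 24 + 36 = 60 months, which is the stated 4-5 years. The sum is internally correct; the 36 is the problem.

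**Step 2: total under the visit schedule.** Total = A + 48.

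| Recruitment A (months) | Timetable, A + 36 | Schedule, A + 48 | Shortfall | Last standard-arm month-18 examination, A + 18 |
|---|---|---|---|---|
| 12 | 48 | 60 | 12 | 30 |
| 18 | 54 | 66 | 12 | 36 |
| 24 | 60 | 72 | 12 | 42 |

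The schedule needs 5-6 years. The shortfall is 12/48 = 25% of the stated duration with one year of recruitment and 12/60 = 20% with two.

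**Step 3: does another reading of 36 work?**

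- As the relaxed arm's interval from first to second examination: 48 − 12 = 36. This probably explains the number. It does not repair the sum, because the only other component is recruitment and the 12 months from the last index procedure to the first examination are still missing.
- As time from the index procedure to the second examination: that is month 18 in the standard arm and month 48 in the relaxed arm. Neither is 36.
- As a total that is right with shorter recruitment: a 4-5 year total with 48 months of follow-up leaves 48 − 48 = 0 to 60 − 48 = 12 months for recruitment, against the stated 1-2 years. Five years is enough only if recruitment takes no more than 12 months.

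**Step 4: what closing on the timetable would cost.** This step rests on two assumptions that are not in the protocol: that the study closes at A + 36, and a shape for accrual. Patients enrolled in the last 12 months of recruitment would then not have reached month 48. Their share is:

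- uniform accrual: 12/A
- linearly falling accrual: (12/A)²
- linearly rising accrual: 1 − ((A − 12)/A)²

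| A (months) | Falling | Uniform | Rising | Relaxed-arm patients affected, of about 380 |
|---|---|---|---|---|
| 12 | 100% | 100% | 100% | 380 / 380 / 380 |
| 18 | 44% | 67% | 89% | 169 / 253 / 338 |
| 24 | 25% | 50% | 75% | 95 / 190 / 285 |

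The last column of the Step 2 table shows that every standard-arm month-18 examination would already have fallen due by A + 36. If month 18 is that arm's SC2, the loss of primary-endpoint examinations would fall on the relaxed arm alone. If the comparison is meant at month 48 in both arms, the loss would be symmetric.

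**The case against.** The strongest reply is that this sentence is a planning estimate. It sets no visit, endpoint, analysis trigger or closing date. The visit schedule is the operative instruction, it is stated consistently, and staff who follow it will perform the month-48 examination whatever the timetable says. On that view the patient-loss figures describe an event that no section announces, under accrual shapes the protocol does not give, and the funding consequence presumes a budget that is not shown.

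A second point concerns the arms. The timetable counts follow-up only as far as SC2. If the standard arm's SC2 is its month-18 examination, 36 months is ample there. That arm is then short only against its additional month-48 colonoscopy.

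Much of this stands as a limit on weight. The certain effect is an understated duration; the data loss and the funding gap are conditional and should be read that way. The arithmetic is untouched. Calling the total anticipated covers uncertainty about recruitment speed, but not the length of follow-up, which the protocol itself fixes. The sentence also speaks of completing the study, and both arms' schedules run to month 48, so the 12-month shortfall against completion applies to both. Which examination is the standard arm's SC2 is a separate question, and this finding does not depend on it.

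**Conclusion.** The concern holds. The timetable contradicts the visit schedule by 12 months: 4-5 years stated, 5-6 years required for the last month-48 examination. This rests only on the protocol's own figures and on month 0 practically coinciding with enrolment. No reading of the 36 months removes the gap.

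The error is worth correcting but does not by itself affect the validity of the comparison. The possible loss of relaxed-arm endpoint examinations, 25% to 100% across the scenarios considered, arises only if the study really closes 36 months after the last enrolment.

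**What to change.** Reconcile the Timetable with the abstract and with Groups and Follow-Up, so that all three carry the same length of follow-up measured from the same starting point. If the visit schedule stands, the Timetable should state 5-6 years: 1-2 years of recruitment plus 48 months of follow-up from the last patient's index procedure. The study would then not be planned to close before the last month-48 examination.

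The change is one sentence. It adds no patients or procedures. Its downside is a stated duration one year longer, with 12 more months of research assistant and database time to fund, which the schedule as written already requires.
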